Inclusion Criteria: Subjects age 18 and older of either sex will be included. Subjects must meet the WASOG definition of pulmonary sarcoidosis. (16) They must have histologically proven sarcoidosis, evidence of Pulmonary sarcoidosis on chest radiograph (Stage I, II, III or IV) (17), an FVC >50%, and can have concomitant extrapulmonary disease. Subjects must require 15 mg to 30 mg/day prednisone or equivalent corticosteroid to control their sarcoidosis. Dose of prednisone must be stable for 4 weeks prior to enrollment in the study. Subjects may be taking methotrexate, but may not be taking other immunosuppressive or immunomodulatory treatments (see below).

Exclusion Criteria:

- Patients taking immunomodulatory medications other than methotrexate in the two months prior to the study period will not be included. This includes but is not limited to azathioprine, cyclophosphamide, leflunomide, mycophenolate mofetil, cyclosporine, tacrolimus, and biologic medications.
- Patients requiring >30 mg/day prednisone or its equivalent.
- Pregnant or lactating women will not be included.
- Subjects with the following blood dyscrasias will not be included:
 - Hemoglobin <9g/dL or Hematocrit <30%
 - White blood cell count <3.0 K/cu mm
 - o Absolute neutrophil count <1.2 K/cu mm
 - o Platelet count <100 K/cu mm
- Subjects with an estimated GFR ≤40 ml/min
- Subjects with a total bilirubin, AST, or ALT more than 1.5 times the upper limit of normal at screening.

- Severe, progressive, or uncontrolled chronic liver disease including fibrosis, cirrhosis, or recent or active hepatitis.
- History of any lymphoproliferative disorder such as Epstein Barr virus (EBV) related lymphoproliferative disorder, history of lymphoma, leukemia, or signs and symptoms suggest of current lymphatic disease.
- Current malignancy or history of malignancy, with the exception of adequately treated or excised non-metastatic basal cell or squamous cell cancer of the skin, or cervical carcinoma in situ.
- Have or have had an opportunistic infection (e.g., herpes zoster [shingles], cytomegalovirus, Pneumocystis carinii, aspergillosis and aspergilloma, histoplasmosis, or mycobacteria other than TB) within 6 months prior to screening.
- Have a known infection with human immunodeficiency virus (HIV)

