 - Malignancy: In the seven controlled trials, during the 0 to 3 months exposure, malignancies excluding NMSC were reported in 0 patients who received placebo and 2 patients (0.3 events per 100 patient-years) who received either Tofacitinib 5 mg or 10 mg twice daily. The rate difference between treatment groups (and the corresponding 95% confidence interval) was 0.3 (-0.1, 0.7) events per 100 patient-years for the combined 5 mg and 10 mg twice daily Tofacitinib group minus placebo. In the seven controlled trials, during the 0 to 12 months exposure, malignancies excluding NMSC were reported in 5 patients (0.4 events per 100 patient-years) who received 5 mg twice daily

Page 9 of 13 Revised: 7/15/2019

of Tofacitinib and 7 patients (0.6 events per 100 patient-years) who received 10 mg twice daily of Tofacitinib. The rate difference between Tofacitinib doses (and the corresponding 95% confidence interval) was 0.2 (-0.4, 0.7) events per 100 patient-years for 10 mg twice daily Tofacitinib minus 5 mg twice daily Tofacitinib. One of these malignancies was a case of lymphoma that occurred during the 0 to 12 month period in a patient treated with Tofacitinib 10 mg twice daily. The most common types of malignancy, including malignancies observed during the long-term extension, were lung and breast cancer, followed by gastric, colorectal, renal cell, prostate cancer, lymphoma, and malignant melanoma

- Gastrointestinal Perforation: Events of gastrointestinal perforation have been reported in clinical studies with Tofacitinib in rheumatoid arthritis patients, although the role of JAK inhibition in these events is not known.
- Laboratory Abnormalities: Treatment with Tofacitinib was associated with initial lymphocytosis at one month of exposure followed by a gradual decrease in mean absolute lymphocyte counts below the baseline of approximately 10% during 12 months of therapy. Lymphocyte counts less than 500 cells/mm3 were associated with an increased incidence of treated and serious infections. Treatment with Tofacitinib was associated with an increased incidence of neutropenia (less than 2000 cells/mm3) compared to placebo. Treatment with Tofacitinib was associated with an increased incidence of liver enzyme elevation compared to placebo. Most of these abnormalities occurred in studies with background DMARD (primarily methotrexate) therapy.

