- Treatment with Tofacitinib was associated with increases in lipid parameters including total cholesterol, low-density lipoprotein (LDL) cholesterol, and high-density lipoprotein (HDL) cholesterol. Maximum effects were generally observed within 6 weeks. The effect of these lipid parameter elevations on cardiovascular morbidity and mortality has not been determined.
 - Lymphopenia: In the controlled clinical trials, confirmed decreases in absolute lymphocyte counts below 500 cells/mm3 occurred in 0.04% of patients for the 5 mg twice daily and 10 mg twice daily Tofacitinib groups combined during the first 3 months of exposure. Confirmed lymphocyte counts less than 500 cells/mm3 were associated with an increased incidence of treated and serious infections.
 - O Neutropenia: In the controlled clinical trials, confirmed decreases in ANC below 1000 cells/mm3 occurred in 0.07% of patients for the 5 mg twice daily and 10 mg twice daily Tofacitinib groups combined during the first 3 months of exposure. There were no confirmed decreases in ANC below 500 cells/mm3 observed in any treatment group. There was no clear relationship between neutropenia and the occurrence of serious infections. In the long-term safety population, the pattern and incidence of confirmed decreases in ANC remained consistent with what was seen in the controlled clinical trials.
 - Liver Enzyme Elevations: Confirmed increases in liver enzymes greater than 3 times the upper limit of normal (3x ULN) were observed in patients treated with Tofacitinib. In patients experiencing liver enzyme elevation, modification of treatment regimen, such as reduction in the dose of concomitant DMARD, interruption of Tofacitinib, or reduction in Tofacitinib dose, resulted in decrease or normalization of liver enzymes. In the controlled monotherapy trials (0-3 months), no differences in the incidence of ALT or AST elevations were observed between the placebo, and Tofacitinib 5 mg, and 10 mg twice daily groups. In the controlled background DMARD trials (0-3 months), ALT elevations greater than 3x ULN were observed in 1.0%, 1.3% and 1.2% of patients receiving placebo, 5 mg, and 10 mg twice daily, respectively. In these trials, AST elevations greater than 3x ULN were

Page 10 of 13 Revised: 7/15/2019

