observed in 0.6%, 0.5% and 0.4% of patients receiving placebo, 5 mg, and 10 mg twice daily, respectively. One case of drug-induced liver injury was reported in a patient treated with Tofacitinib 10 mg twice daily for approximately 2.5 months. The patient developed symptomatic elevations of AST and ALT greater than 3x ULN and bilirubin elevations greater than 2x ULN, which required hospitalizations and a liver biopsy.

- Lipid elevations: In the controlled clinical trials, dose-related elevations in lipid parameters (total cholesterol, LDL cholesterol, HDL cholesterol, triglycerides) were observed at one month of exposure and remained stable thereafter. Changes in lipid parameters during the first 3 months of exposure in the controlled clinical trials are summarized: Mean LDL cholesterol increased by 15% in the Tofacitinib 5 mg twice daily arm and 19% in the Tofacitinib 10 mg twice daily arm. Mean HDL cholesterol increased by 10% in the Tofacitinib 5 mg twice daily arm and 12% in the Tofacitinib 10 mg twice daily arm. Mean LDL/HDL ratios were essentially unchanged in Tofacitinib-treated patients. In a controlled clinical trial, elevations in LDL cholesterol and ApoB decreased to pretreatment levels in response to statin therapy. In the long-term safety population, elevations in lipid parameters remained consistent with what was seen in the controlled clinical trials.
- Serum creatinine elevations: In the controlled clinical trials, dose-related elevations in serum creatinine were observed with Tofacitinib treatment. The mean increase in serum creatinine was <0.1 mg/dL in the 12-month pooled safety analysis; however, with increasing duration of exposure in the long-term extensions, up to 2% of patients were discontinued from Tofacitinib treatment due to the protocol-specified discontinuation criterion of an increase in creatinine by more than 50% of baseline. The clinical significance of the observed serum creatinine elevations is unknown.
- Other adverse reactions: The following occurred in at least 2% or more of patients and at least 1% greater than that observed in patients on placebo:

	Tofacitinib 5 mg Twice Daily	Tofacitinib 10 mg Twice Daily*	Placebo			
Preferred Term	N = 1336 (%)	N = 1349 (%)	N = 809 (%)			
Diarrhea	4.0	2.9	2.3			
Nasopharyngitis	3.8	2.8	2.8			
Upper respiratory tract infection	4.5	3.8	3.3			
Headache	4.3	3.4	2.1			
Hypertension	1.6	2.3	1.1			
N reflects randomized and treated patients from the seven clinical trials						

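### Section 11a ties lymphocyte counts below 500 cells/mm3 to infection, but neither the blood-count exclusions nor the discontinuation list sets a lymphocyte limit: a small safety gap that is cheap to close

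*Combined protocol and SAP*

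**What the plan says.** Section 11a, under Laboratory Abnormalities, states: "Lymphocyte counts less than 500 cells/mm3 were associated with an increased incidence of treated and serious infections". The Lymphopenia item that follows repeats the link for confirmed counts. The same section describes the time course as "initial lymphocytosis at one month of exposure followed by a gradual decrease in mean absolute lymphocyte counts below the baseline of approximately 10" per cent, over 12 months of therapy. It gives the frequency in the first three months, with both doses combined: "confirmed decreases in absolute lymphocyte counts below 500 cells/mm3 occurred in 0.04% of patients".

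For neutrophils, Section 11a says: "There was no clear relationship between neutropenia and the occurrence of serious infections". It also reports that "confirmed decreases in ANC below 1000 cells/mm3 occurred in 0.07% of patients" over the same period.

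The Section 5b blood-count exclusions are haemoglobin below 9 g/dL or haematocrit below 30%, "White blood cell count <3.0 K/cu mm", "Absolute neutrophil count <1.2 K/cu mm", and platelets below 100 K/cu mm. The Section 6 discontinuation list sets blood-count stops for neutrophils below 1000/mm3, platelets below 100,000/mm3, and haemoglobin below 8.0 g/dL or at least 2 g/dL under baseline. Lymphocyte counts appear nowhere outside the risk section. Section 10 consists of a pointer to a separate Data Safety Monitoring Plan.

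**The concern.** The protocol names a lymphocyte level that it associates with infection, then attaches no entry rule and no stopping rule to it in the two lists where such rules sit. Neutrophils have both kinds of rule, although the protocol reports no clear tie between neutropenia and serious infection. The neutrophil rules are sensible and should stay. The contrast only shows that the lymphocyte count was left out.

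The stake is subject safety. Every subject starts tofacitinib while taking 15 to 30 mg/day of prednisone, and methotrexate is allowed. Section 11a notes that some infected patients had disseminated disease and were often taking such agents. It also says that risks in sarcoidosis may differ from those in rheumatoid arthritis. Subjects who meet the primary endpoint may stay on drug for up to a further year. The serious-infection stop in Section 6 acts only once the infection has happened.

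Nothing here bears on how the primary endpoint is analysed.

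**Working it through.** The protocol states no figure to reproduce on this point. The check has three parts.

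**1. Do the existing entry limits imply a lymphocyte floor?** Lymphocytes cannot exceed white cells minus neutrophils. The limits are white cells not below 3.0 K and neutrophils not below 1.2 K (Section 5b).
- White cells 3.0 K, neutrophils 2.6 K: at most 3.0 − 2.6 = 0.4 K lymphocytes. Both limits are passed.
- White cells 8.0 K, neutrophils 7.6 K: at most 8.0 − 7.6 = 0.4 K. Both limits are passed, because neutrophils have no upper limit.

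Both are below 0.5 K (500 cells/mm3), so no floor is implied. These constructed cases show that entry is possible, not how often it would occur.

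**2. How likely is a case among five subjects?** The chance of at least one is 1 − (1 − p)^5.

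| Event, first 3 months, rheumatoid arthritis | p (Section 11a) | At least one in 5 |
|---|---|---|
| Lymphocytes below 500 | 0.0004 | 1 − 0.9996^5 = 0.20% |
| Neutrophils below 1000 | 0.0007 | 1 − 0.9993^5 = 0.35% |

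The two rates are of the same order, so rarity alone does not explain why only neutrophils have a mandatory stop.

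For precision, I assume that the denominators are those of the adverse-reaction table in Section 11a, whose footnote says "N reflects randomized and treated patients from the seven clinical trials". The two tofacitinib groups total 1336 + 1349 = 2685. Then 1/2685 = 0.037%, which rounds to 0.04%, and 2/2685 = 0.074%, which rounds to 0.07%. The lymphocyte rate would therefore be a single patient. The exact (Clopper-Pearson) 95% interval for 1/2685 is 0.00094% to 0.207%. At the upper bound the chance among five subjects is 1 − (1 − 0.00207)^5 = 1.03%.

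**3. Would the described mean fall take a subject below 500?** A 10% fall crosses 500 only from a baseline under 500/0.9 = 556 cells/mm3. A typical subject would not get there. The gap therefore matters mainly for someone who enters already low, and for the extension. The 0.04% figure covers neither, and the documents give no rate for either.

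**The case against.** The strongest reply is that the risk is tiny and already watched. Blood counts are taken at baseline, at weeks 2, 4, 8, 12 and 16, and every two months in the extension, so investigators will see the lymphocytes. Recent opportunistic infection and known HIV are exclusions, screening includes tuberculosis and hepatitis tests, and the investigator may stop the drug for serious or severe adverse events. The described course is a rise at one month and then a slow fall, so most of the 16 weeks may lie outside the period of concern. The association is stated without infection rates above and below 500, so the harm avoided cannot be sized.

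All of this stands as a limit on size. It does not fill the gap, because none of these safeguards sets a lymphocyte number at entry or on treatment.

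Two stronger readings are tempting and are not supported:
- A reader might infer that the trial has no lymphocyte action level at all. The documents show this only for the two lists. Laboratory action levels could sit in the Data Safety Monitoring Plan, which was not available.
- A reader might infer that the risk is material because these subjects take steroids. Assumed rates of 1%, 5% and 10% would give a 4.9%, 22.6% and 41.0% chance of a case among five subjects. No rate of that size appears in the documents, so those figures should not raise the grading.

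**Conclusion.** The point holds as a low-magnitude safety improvement. The two lists let a subject below the protocol's own infection-linked level enter and remain on treatment without a pre-set lymphocyte action. On the documented rate, the chance of any such fall among five subjects is about 0.20%, and at most about 1.03% if the denominator assumption in the working is right. That rate comes from rheumatoid arthritis, pools two doses and covers three months. Subjects who enter low and exposure in the extension remain unquantified. The conclusion is confined to Sections 5b and 6 and would need revisiting if the Data Safety Monitoring Plan sets a level. It is not a fatal flaw. It is worth correcting because the protocol itself names the threshold and the change costs almost nothing.

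**What to change.** Keep every current blood-count limit, and make these changes:

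1. **Section 5b:** add *absolute lymphocyte count <500 cells/mm3* to the blood-count exclusions. The documents give no basis for a different value.
2. **Section 6:** add *absolute lymphocyte count <500 cells/mm3, confirmed on prompt repeat: discontinue*. State that tofacitinib is held and the steroid taper paused until the repeat result, that a hold alone is not a withdrawal, and that a held subject is still assessed for the endpoint at week 16.
3. **Scope:** apply the stopping rule in both the 16-week study and the extension.
4. **Consistency:** if the Data Safety Monitoring Plan already sets a lymphocyte level, align the two lists with it.

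The cost is one entry in each list plus the hold instructions. The neutrophil rules already need a differential count, so no new scheduled draw is required. The downside is a rare repeat test, exclusion or withdrawal. Section 6 pairs discontinuation with withdrawal, and one withdrawal is 1/5 = 20% of a sample whose success rule is 3 of 5. That is why the rule should require confirmation before stopping.
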